## 1. INTRODUCTION

### 1.1. Indication

The purpose of this study is to assess safety and efficacy of treatment with pregabalin in patients with idiopathic small fiber neuropathy proven by skin biopsy.

### 1.2. Background and Rationale

Pregabalin is an alpha-2-delta (a2d) ligand that has analgesic, anxiolytic, and anticonvulsant activity. It has demonstrated anti-nociceptive activity in animal models of neuropathic pain and in patients with painful diabetic painful neuropathy (DPN), post-herpetic neuralgia (PHN), and fibromyalgia. Pregabalin (Lyrica) is approved for the treatment of neuropathic pain in the European Union and Canada, and for the management of neuropathic pain associated with DPN and PHN in the United States and South Africa. Pregabalin has been shown to be an effective treatment for other indications, including generalized anxiety disorder, and central neuropathic pain associated with spinal cord injury.

Small fiber neuropathy is a sub-type of sensory neuropathies that predominantly affects the small unmyelinated fibers. Small fiber neuropathy has been defined as “peripheral neuropathy manifest by paresthesias with findings of small-fiber dysfunction on neurologic examination”[1]. Paresthesia is often painful in these patients and signs of involvement of large fibers are absent or minimal. Patients typically present with positive sensory symptoms, including tingling, burning, shooting pain, or aching. The pain is often worse at night and may interfere with sleep. Patients may also have negative symptoms, including numbness, feeling of tightness around the feet, and coldness. Symptoms are usually distal and length-dependent [2]. The exam findings often include a reduction in sensitivity to pain and temperature along with normal strength, proprioception, and tendon reflexes.

Diagnostic electrophysiologic studies are often performed in patients with suspected small fiber neuropathy to rule out the presence of large fiber neuropathy. The routine nerve conduction studies are often normal [3]. Skin biopsy with quantification of epidermal nerve fibers and sweat glands is an effective way to diagnose small fiber neuropathy[4]. Quantitation of epidermal nerve fibers has a positive predictive value of 75% and a negative predictive value of 90%, with a diagnostic efficiency of 88% for patients with sensory neuropathies[5]. The sensitivity (74–90%) and specificity (64–90%) of skin biopsy for diagnosis of small fiber neuropathy is high[6]. Therefore, consensus guidelines have recommended skin biopsy as preferred method to establish diagnosis of small fiber neuropathy[7]. IENFD is an unbiased pathological measure of c-fiber nociceptors that is increasingly used as an outcome measure in human clinical trials. These fibers express TRPV1 and therefore are important in pain perception and painless injuries. In cross sectional studies IENFD is reduced in many neuropathic populations including people with HIV infection, diabetes, Fabry disease and genetic amyloid. In some instances morphological changes of nerve fibers such as large swellings have been associated with subsequent nerve fiber loss. Decreases or loss of IENFD has been correlated with increases in heat pain and cold thresholds. IENFD correlates with unmyelinated nerve fiber counts derived from electron microscopy studies of sural nerve biopsies and led to an editorial in Neurology

that concluded that skin biopsies should replace sural nerve biopsies in patients with normal nerve conduction test results. Epidermal nerve fibers are affected early in the course of most peripheral neuropathies compared to large myelinated nerve fibers. This is postulated to represent the increased metabolic demands that small unmyelinated nerve fibers are under to maintain a membrane potential. Thus a reduction in IENFD is often the only objective evidence of neuropathy in patients with early HIV-associated sensory neuropathy or early diabetic neuropathy. IENFD also offers a confirmatory documentation that a patient with painful feet actually has a peripheral neuropathy and not another condition that could mimic neuropathy.

Skin biopsy has been instrumental in defining a population of patients with painful peripheral neuropathy and relatively normal examinations and no known etiology for their neuropathy. Such patients are often labeled as having idiopathic small fiber neuropathy and typically complain of numbness, burning pain, paresthesias, or allodynia in the feet, usually with cutaneous sensory loss but with an otherwise normal neurologic examination. Small fiber neuropathy remains idiopathic in large number of patients despite extensive laboratory testing, especially in adults over 60 years old[8]. Diabetes, impaired glucose tolerance test, alcohol, Sjogren syndrome, medications, toxins, HIV infection, amyloidosis, Tangier disease, and Fabry's disease are among identifiable causes of small fiber neuropathy. The incidence and prevalence of small fiber neuropathy is not well known. One study from Netherlands suggested an overall minimum incidence over of 11.73 cases/100,000/year and an overall minimum prevalence of 52.95 cases/100,000 [9].

Small fiber neuropathy has been shown to have a detrimental effect on quality of life and to be a major source of disability [10]. Bakkers et al reported that idiopathic small fiber neuropathy can be as disabling as neuropathy caused by diabetes mellitus or other forms of small fiber neuropathy with an identifiable cause. Patients with small fiber neuropathy have ongoing, sometimes excruciating pain and experience continuous difficulty dealing with the consequences of their illness, causing severe reduction in all aspects of quality of life. A study of 100 patients diagnosed with idiopathic small fiber neuropathy showed that these patients experience moderate to severe pain, which negatively impacts health status, function, and productivity, and leads to substantial direct and indirect costs [11].

Treatment of idiopathic small fiber neuropathy is mostly symptomatic. Unfortunately, there is no direct evidence for treating idiopathic small fiber neuropathy and most of the medications currently used are based on the assumption that evidence from small fiber neuropathy due to diabetes, HIV or other causes can be generalized to idiopathic cases [12]. However, studies in the past have shown that this generalization is not always successful, as we learned that some medications that are useful in diabetic induced small fiber neuropathy are not that effective for cases caused by HIV infection [13].

Pregabalin has been used for treatment of painful small fiber neuropathy caused by diabetes. Multiple studies have shown safety and efficacy of pregabalin in controlling pain in patients with diabetic neuropathy. However, very few of these studies have patients with skin biopsy proven small fiber neuropathy. In a study of 157 patients with neuropathic pain from various etiologies (diabetes, HIV, post-trauma, etc), Gilron et al used an enriched enrollment protocol [14, 15] to

study the effect of pregabalin on pain score and reported a modest but significant effect. Only 8 patients in their treatment group had idiopathic small fiber neuropathy and they did not use skin biopsy to confirm the diagnosis [16]. In a double-blinded randomized control trial of pregabalin in HIV-induced painful small fiber neuropathy, pregabalin was well tolerated but was not superior to placebo in pain control [17]. In a meta-analysis of 11 randomized controlled trial of pregabalin in treatment of neuropathic pain in elderly patients, the drug was shown to be effective and safe with dizziness, somnolence, peripheral edema, asthenia, dry mouth, weight gain, and infections being most common side effects [18]. However, they did not report the number of patients with idiopathic small fiber neuropathy.

Since idiopathic small fiber neuropathy is a relatively common and disabling disorder, there is a need to develop treatment strategies and identify medications that can ameliorate pain, improve function and quality of life. Currently, there is no evidence regarding best treatment options for idiopathic small fiber neuropathy. Additionally, most of the studies that have examined the efficacy of various treatment options including Pregabalin on neuropathic pain did not use an objective and quantitative measure of small fiber neuropathy such as skin biopsy to select their study subjects. This might create a dilutional effect on the efficacy measures since some of the included subjects might have pain that is not originated from a neuropathic process. Since pregabalin has been shown to be a cost effective treatment for some types of small fiber neuropathy such as diabetic neuropathy [19] and improves quality of life [20], it would be a valuable therapeutic option for idiopathic small fiber neuropathy if proven effective. However, there is no study directly examining the effect of pregabalin on idiopathic, skin biopsy proven small fiber neuropathy. Therefore, we aim to study the effect of pregabalin on pain control specifically in a group of patients with idiopathic small fiber neuropathy proven by skin biopsy in a partially enriched enrollment plan. This design would allow us to improve upon previous studies in several aspects. Using skin biopsy as inclusion criteria would prevent recruitment of patients that might have non-neuropathic pain and therefore confound the data. Using a partial enrichment plan would help us to exclude patients who are non-respondent to treatment and increase the power of study.

Enriched enrollment with randomized withdrawal design is recommended by The Initiative on Methods, Measurement, and Pain Assessment in Clinical Trials (IMMPACT), comprising experts in the design and evaluation of treatments for chronic pain, in efficacy studies (Dworkin, et al 2010). Patients exhibiting a response to treatment for neuropathic pain defined as a 30% or greater reduction in neuropathic pain from baseline (and mean NRS pain intensity  $\leq 7$ ) will be randomized in this study if they have met all inclusion and no exclusion criteria. The 30% pain reduction criteria is consistent with publications which characterize this as substantial improvement in pain (Dworkin et al, 2008; Farrar, et al 2001) and with evidence that enrichment based on this response criteria is consistent with good assay sensitivity in a neuropathic pain population (Hewitt 2011). Durability of effect (ie, time to efficacy failure) will be assessed in the randomized withdrawal phase of the study by using the time to efficacy failure definition of the first 3 days of at least 30% increase in pain intensity relative to final maintenance week of single blind treatment phase and mean 24 hour pain intensity level  $> 4.0$  (or discontinuation due to lack of efficacy).

The safety and tolerability of pregabalin has been examined several clinical studies. Pregabalin has been or is currently being investigated in over 102 clinical controlled and uncontrolled Phase 2/3 studies. These studies have been conducted in 3 different therapy areas: pain, epilepsy, and psychiatric indications (anxiety disorders and acute mania). In the controlled studies, doses of 50 to 600 mg/day of pregabalin administered in 2 or 3 divided doses per day were evaluated for efficacy and safety. The most common adverse events reported are dizziness (30%), somnolence (18%), headache (12%), and weight increase (10%).

## **2. STUDY OBJECTIVES AND ENDPOINTS**

### **2.1. Objectives**

#### **Primary Objective:**

To evaluate the efficacy of pregabalin (150-600 mg/day, flexibly administered BID) compared with placebo for the treatment of pain associated with idiopathic distal symmetrical small fiber peripheral neuropathy.

#### **Secondary Objectives:**

1. To evaluate the efficacy of pregabalin compared with placebo on global assessment of treatment ;
2. To evaluate the efficacy of pregabalin compared with placebo on quality of life ;
3. To explore the relationship between proteomics and lipidomics profile and treatment response;
4. To explore the relationship between metabolite profile and treatment response;
5. To assess the safety and tolerability of pregabalin.

### **2.2. Endpoints**

#### **Primary Efficacy Endpoint**

Mean endpoint 24-h average pain intensity based on pain intensity scores after 12 weeks maintenance treatment phase.

#### **Secondary Measures and Efficacy Endpoints**

1. Brief Pain Inventory (BPI-sf);
2. Daily Sleep Interference Rating Scale (SIRS);
3. Patient Global Impression of Change (PGIC);
4. EuroQoL 5-Dimensions (EQ-5D);
5. Small Fiber Neuropathy Symptom Inventory Questionnaire (SFN-SIQ);

[figure not shown]
## 6. Proteomics, lipidomics and metabolite exploratory analysis for treatment response.

### Safety and other Diagnostic Assessments

- Adverse events monitoring;
- Physical exam/Neurological exam;
- Vital signs;
- Suicidality Assessment (C-SSRS).

### 3. STUDY DESIGN

This enriched enrollment randomized withdrawal study comprises 4 phases: a screening and selection phase, a 2-4 weeks washout period from previous pain medication for enriched enrollment, an 8 week single-blind pregabalin treatment phase; and a 4 week randomized withdrawal phase. Patients who show any increase in their pain intensity score during the washout phase will be eligible for the single blind pregabalin treatment phase. Patients who respond to pregabalin, with at least 1 point improvement in neuropathic pain from baseline at the end of the single-blind pregabalin treatment phase and meeting all other study requirements are considered eligible for participation in the withdrawal phase. These eligible patients are randomly assigned (1:1) to continue pregabalin or to be switched to placebo for a comparison of pregabalin efficacy and safety. Patients who have a worsening of average pain relative to the last week of the single blind pregabalin treatment period by more than one point and average pain level  $\geq 4$  will be considered to have a loss of therapeutic response (LTR).

\*Low creatinine clearance patients: 150-300 mg/day

## **4. SUBJECT SELECTION**

This study can fulfill its objectives only if appropriate subjects are enrolled. The following eligibility criteria are designed to select subjects for whom protocol treatment is considered appropriate. All relevant medical and non-medical conditions should be taken into consideration when deciding whether this protocol is suitable for a particular subject.

### **4.1. Inclusion Criteria**

Subject eligibility should be reviewed and documented by an appropriately qualified member of the investigator's study team before subjects are included in the study.

Subjects must meet all of the following inclusion criteria to be eligible for enrollment into the study:

1. Evidence of a personally signed and dated informed consent document indicating that the subject (or a legal representative) has been informed of all pertinent aspects of the study;
2. Subjects who are willing and able to comply with scheduled visits, treatment plan, laboratory tests, and other study procedures and are able to read and participate in all study assessments;
3. Subjects with idiopathic predominate-small fiber neuropathic pain based on medical history, neurological examination, and punch biopsy results. Diagnosis of small fiber neuropathy is based on presence of at least 2 of the following symptoms, one of the following signs and abnormalities in skin biopsy consistent with small fiber neuropathy. Idiopathic small fiber neuropathy is defined as ruling out presence of diabetes, HIV infection and other conditions listed in exclusion criteria;

#### **a. Symptoms:**

- Burning pain in feet
- Numbness
- Tingling (pins and needles)
- Hypersensitive to touch, heat, or cold

#### **b. Signs**

- Allodynia (mechanical brush)
- Diminished perception of pain with pinprick
- Hyperalgesia to pin prick
- Diminished temperature sensation (cold or heat)

4. Subject must have chronic peripheral neuropathic pain consistent with predominately small fiber neuropathy. Pain history indicates that pain started in the feet or legs and has been present for more than 3 months;
5. A score >3 and <8 on Pain intensity scale for pain in prior week at first visit;
6. Show increase in pain intensity scores during the 2 weeks of wash off period;
7. Age older than 18 years;

#### **4.2. Exclusion Criteria**

Subjects presenting with any of the following will not be included in the study:

1. Subjects with large-fiber predominant neuropathy defined as sural SNAP amplitude less than 6  $\mu$ V or Peroneal CMPA recorded at EDB of less than 1 mV;
2. Subjects with peripheral neuropathic pain secondary to specific etiologies including HIV infection, trigeminal neuralgia (TGN), carpal tunnel syndrome (CTS), toxic neuropathy (e.g. chemotherapy exposure), paraneoplastic neuropathy, monogamopathy, inflammatory neuropathy, celiac disease, systemic lupus, peripheral vascular disease, connective tissue disorders, hepatitis C, Fabry disease, and diabetes;
3. Subjects with uncontrolled thyroid or B12 disorders (subjects with a history of thyroid or B12 disorders currently taking replacement therapy with normal screening values are allowed);
4. Subjects with pain due to Complex Regional Pain Syndrome (CRPS, Type I or Type II);
5. Subjects with skin conditions in the affected area that in the judgment of the investigator could interfere with evaluation of neuropathic pain condition;
6. Pain that is not present in both feet/legs (ie, pain is not bilateral);
7. Patients with only negative symptoms defined as numbness without clear evidence of spontaneous pain either constant or episodic;
8. Subjects with pain that is not present every day (chronic) or where pain description does not have a classic stocking distribution per the clinical assessment with clinician (pain may vary in severity during the day);
9. Subjects with other pain that may confound assessment or self-evaluation of the peripheral neuropathic pain such as back pain, radicular pain, and fibromyalgia;

10. Subjects who have failed pregabalin treatment due to lack of efficacy with an adequate course of therapy (doses greater than 150 mg/day for at least 4 week), have hypersensitivity or intolerance to pregabalin or gabapentin, or participated in a pregabalin clinical trial at any time. Subjects that have failed to respond to more than 3 drug treatment trials of adequate dose/duration;
11. Any subject considered at risk of suicide or self-harm based on investigator judgment and/or the details of a risk assessment;
12. Use of prohibited medications in the absence of appropriate washout periods;
13. Subjects with any clinically unstable cardiovascular (including a myocardial infarction in the 3 months prior to Visit 1), hematological, autoimmune, endocrine, renal, hepatic (including chronic hepatitis B, hepatitis B within the past 3 months or ALT or AST > 3X ULN), respiratory, or gastrointestinal disease; epilepsy, symptomatic peripheral vascular disease including intermittent claudication, pernicious anemia, untreated hypothyroidism, venous insufficiency, spinal stenosis, or HIV infection;
14. Other severe acute or chronic medical or psychiatric condition or laboratory abnormality that may increase the risk associated with study participation or investigational product administration or may interfere with compliance or the interpretation of study results and, in the judgment of the investigator, would make the subject inappropriate for entry into this study;
15. Subjects who have had a diagnosis of malignancy other than basal cell carcinoma or carcinoma in situ of the cervix within the past 5 years;
16. Subjects with creatinine clearance (CLcr)  $\leq$ 60 mL/min (estimated prior to Visit 2 from serum creatinine obtained at Visit 1, body weight, age, and gender using the Cockcroft and Gault equation); Subjects who have an estimated CLcr  $\leq$ 60 mL/min by this screening method may have their CLcr measured, at the investigator's discretion, with a 24-hour urine collection performed at the central laboratory. If this 24-hour urine CLcr is  $>$ 60 mL/min, the subject may be eligible. Subjects on dialysis are not eligible;
17. Subjects with a current diagnosis (DSM-IV-TR) of current major depression, history of bipolar diagnosis, or any diagnosis of a psychotic disorder;
18. History of known analgesic or illicit drug abuse within 12 months of first visit;
19. Patients that meet the DSM-IV criteria for alcohol abuse or dependence in the last two years;

20. Subjects with pending Worker's Compensation, Worker's Compensation, civil litigation or disability claims pertinent to the subject's based upon trauma; current involvement in out-of-court settlements for claims pertinent to subject's trauma;
21. Participation in other interventional studies within 28 days before the current study begins and/or during study participation;
22. Pregnant females; breastfeeding females.

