#### **4.4. Life Style Guidelines**

Subjects should not initiate or alter an exercise regimen during the study, as this could influence efficacy results based on the pain scale scores.

Subjects should not modify stable medication regimens, and should not have surgery or interventional medical procedures for the duration of the study.

Female patients at child bearing age must be informed that pregabalin is a category C medication for pregnancy which means that a risk cannot be ruled out and therefore use of an effective birth control method is recommended.

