## **6. STUDY PROCEDURES**

### **6.1. Screening/Visit1**

This is the clinic visit during which a new patient is diagnosed with idiopathic small fiber neuropathy or a patient who has been diagnosed with idiopathic small fiber neuropathy from peripheral neuropathy registry has presented for follow up and is informed about the study.

Informed consent procedures must be completed prior to initiating any study procedures during this visit. Visit 1 must occur between 14 days and 30 days prior to Visit 2, based on the amount of time required for screening procedures or washout period. The duration between Visits 1 and 2 will typically be approximately 14-30 days. A minimum 14 days is required to allow the washout phase.

The following procedures are to be performed at Visit 1. These procedures are not required to occur on the same day, but all results must be available by Visit 2.

- Informed consent
- Medical history, concomitant medications, prior treatments for neuropathy, any non-drug treatments, and adverse events will be reviewed.
- Weekly pain intensity score (1-week recall period) is completed by the patient
- Physical exam and neurological examination are performed, including height, weight, heart rate and blood pressure
- SFN-SIQ
- BPI-sf
- EQ-5D
- Laboratory assessments are performed
- Columbia Suicidality Severity Rating Scale(C-SSRS) baseline and PHQ-8 are completed and reviewed
- Skin Biopsy if not performed previously

If the patient continues to meet entry criteria for the study following the completion of these procedures, the following will be completed:

- The patient will be instructed to complete a pain and sleep diary daily. A sample diary is to be completed and IVRS procedures reviewed with the patient to ensure comprehension.
- Blood draw to collect sample for proteomics and lipidomics.
- The patient will be instructed how to discontinue the current disallowed pain medication and will be scheduled to come to the clinic for Visit 2.

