## **6.2. Treatment Phase**

### **6.2.1. Visit 2 – Clinic Visit**

- Review concomitant treatments, adverse events, and any non-drug treatments.
- Review laboratory results and Visit 1 assessments for eligibility.
- Review daily pain and sleep diaries for compliance and eligibility.
- Perform the following assessments: BPI-SF, SFN-SIQ and EQ-5D
- Review the study entry criteria to determine if the patient meets all inclusion and exclusion criteria (Section 4). Patients not meeting eligibility criteria should not complete the other assessments listed for this visit and will not continue in the trial.

For patients meeting study entry criteria, the following procedures will be performed:

- The patient will be reminded to continue completing daily pain and sleep IVRS diaries each evening.
- Study medication will be dispensed. Blinding must be maintained with the patient. If a supply is being dispensed to last through the next clinic visit (Visit 6/Week 4), instruct the patient regarding which bottle to use, and to take one capsule in the morning and once daily in the evening from a single bottle. The patient will be instructed to begin dosing the following morning.
- Schedule a telephone Visit for Day 7.

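### Pregnant women are excluded, but no pregnancy test is scheduled before pregabalin is dispensed, so an unrecognised pregnancy would not be detected

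*Combined protocol and SAP*

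**What the plan says.** Section 4.2, item 22, excludes "Pregnant females; breastfeeding females". Section 4.1, item 7, admits anyone who meets "Age older than 18 years", with no upper age limit and no restriction by sex. Section 4.4 speaks directly to women of childbearing age. They are to be told that "pregabalin is a category C medication for pregnancy which means that a risk cannot be ruled out", and that "use of an effective birth control method is recommended".

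Eligibility is checked twice. At Visit 1 (Section 6.1) a medical history is taken, "Laboratory assessments are performed", and "all results must be available by Visit 2". At Visit 2 (Section 6.2.1) staff look over those results and are told to "Review the study entry criteria to determine if the patient meets all inclusion and exclusion criteria". Pregabalin is then dispensed: "The patient will be instructed to begin dosing the following morning".

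Section 8.3 lists exposure during pregnancy among the sources of adverse events. Section 8.11.1 puts reports of it on the 24-hour serious-event timeline.

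**The concern.** The plan excludes pregnancy, acknowledges a possible risk to it and requires rapid reporting if exposure occurs. It schedules no test that would find a pregnancy before the first dose. A woman who does not know she is pregnant would answer every history question truthfully and pass both eligibility checks.

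Randomisation gives no protection, because every patient who enters treatment receives pregabalin for the 8-week single-blind phase first. What is at stake is avoidable fetal exposure.

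**Working it through.** The plan gives no figure to reproduce. The check is a reading of every place where a test could be listed, followed by short arithmetic on exposure.

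**1. Is a pregnancy test listed anywhere?**

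| Place | What it contains | Pregnancy test |
|---|---|---|
| Section 6.1 (Visit 1) | History, examinations, questionnaires, laboratory work in general terms | None |
| Section 7.4.1 (Visit 1 panel) | Haematology, chemistry, fasting glucose and HbA1C, TSH, B12/folate, HIV, hepatitis C, ESR, syphilis, creatinine clearance | None |
| Section 6.2.1 (Visit 2) | Review of Visit 1 results and of all criteria; no new laboratory sample | None |
| Sections 6.2.2 to 6.2.6 (Visits 3 to 7) | Visits 3 to 5 by phone unless the investigator decides otherwise; Visits 6 and 7 in clinic | None |
| Sections 7.4.2 to 7.4.4 | Physical and neurological examination, vital signs | None |
| Section 8 | Reporting of exposure during pregnancy | None |
| Appendix 1 | Clinical labs marked at Visit 1 only; no pregnancy row | None |

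The count is 0 across the four clinic visits (1, 2, 6 and 7). These sections show no redaction mark where such an item would sit.

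**2. What remains to apply exclusion 22?** The Visit 1 history and the Visit 2 re-review. That is enough for breastfeeding and for a known pregnancy. It is not enough for an unrecognised one.

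**3. How long could the exposure last?** Take a pregnancy present at Visit 2 and not recognised. The inputs are an 8-week single-blind phase and a 4-week withdrawal phase (Section 3), Visit 7 at day 84 (Appendix 1) and a 7-day taper (Appendix 3).

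- Not randomised after the single-blind phase: 8 × 7 = 56 days, plus 7 = 63 days.
- Pregabalin arm: 12 × 7 = 84 days, plus 7 = 91 days.
- Placebo arm: at least 56 + 7 = 63 days, because the first withdrawal week is an active taper (Section 5). Section 6.2.6 also hands out a taper bottle at Visit 7 without distinguishing arms, so the documents do not fix the total.

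These are upper figures on nominal visit days. Visits 6 and 7 each have a window of ±3 days. Earlier recognition shortens the exposure, and Section 5 waives the taper for some patients. The heading of Section 6.2.6 places Visit 7 at Week 14; the Appendix 1 timing is used here because it agrees with the 8 + 4 weeks of Section 3.

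**4. What would a Visit 2 test add to a Visit 1 test?** It covers conceptions since the screening blood draw. Visit 1 falls 14 to 30 days before Visit 2, so that interval can reach about 30 days. It has no firm minimum, because Visit 1 procedures need not fall on one day (Section 6.1) and screening may be split into two visits (Appendix 1, footnote a).

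**The case against.** The strongest reply is that the criterion can still be applied. History is a legitimate way to apply an exclusion, and several others (such as recent drug abuse, pending claims or participation in another study) have no laboratory test either. That stands. A reader might infer that exclusion 22 cannot be enforced at all, and the documents do not support this: Section 6.1 takes a history and Section 6.2.1 re-checks every criterion. The gap is confined to pregnancies the woman does not know about.

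Nor is pregnancy the one exclusion left without a test. The Section 7.4.1 panel is not a test-per-criterion map. It has nothing for hepatitis B, celiac disease, lupus or Fabry disease, and no nerve conduction study is scheduled for the thresholds in exclusion 1. The case therefore rests on the hazard and the low cost of a test, not on pregnancy being singled out.

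It is also fair to say that few participants may be fertile. Section 1.2 notes that the idiopathic form is especially common over age 60, and only 40 randomised patients are planned. The documents give no count of women of childbearing potential, so the chance of an exposure cannot be estimated. The fix applies only to those women, however, so its cost falls in step.

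Finally, sites may test by habit, and the consent form, which is not in the reviewed text, may say more. Nothing in the protocol requires a test.

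**Conclusion.** The concern holds as a participant-safety gap that should be closed. No pregnancy test is scheduled before first dosing, and history alone cannot detect an unrecognised pregnancy. Exposure could reach about 8 weeks plus taper (63 days) without randomisation, and about 12 weeks plus taper (91 days) in the pregabalin arm. These figures assume that the pregnancy is present at Visit 2 and stays unrecognised, that visits fall on the Appendix 1 days and that the full taper is taken. They describe duration, not likelihood.

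Two stronger readings should be resisted. One is that a Visit 2 test always gains at least 14 days over a screening test; split screening visits remove that floor. The other is that the trial's efficacy result is at risk. The ANCOVA in Section 9.1.1 and the sample size in Section 9.1 do not depend on this point.

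**What to change.** For women of childbearing potential only:

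1. Add a pregnancy test to the Visit 1 panel in Section 7.4.1, run on blood already drawn at screening.
2. Add a urine pregnancy test to Section 6.2.1, with a negative result required before study medication is dispensed. Dosing does not start until the next morning, so this delays nothing.
3. Add a pregnancy-test row to Appendix 1, marked at Visits 1 and 2.

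The cost is one assay on an existing sample, one urine test at an existing clinic visit and an occasional confirmatory test after a positive or doubtful result. A very recent conception could still be missed at Visit 2. Conception during treatment is not addressed; for that, the contraception advice in Section 4.4 remains the only provision.
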